## G

**G1. Statistical analysis:** Preliminary analyses will include analysis of variance and chi square tests that focus on ensuring that the groups are similar at baseline. The primary analytic approach will be analysis of covariance in which the dependent variable will be the post intervention value of the outcome measure

and the independent variables will be the study group and the baseline value of the outcome. This will allow us to test hypotheses about the equality of post intervention values after adjusting for the baseline value. In these analyses, we will be specifically interested in the statistical contrasts that compare the groups with and without TUDCA. The appropriateness of all analysis of variance and covariance models will be evaluated using regression residuals. If normality or homoscedasticity requirements are violated, data transformations will be explored and, if appropriate transformations cannot be found, analyses may be done semi-parametrically using the ranks of the data.

**G2. Power Estimates for each primary endpoint:** We have conservatively estimated the improvements in our primary endpoints. *We plan to include 24 subjects in each group and conservatively estimate a 33% drop-out rate.* These drop-out rates are greater than those seen in our prior studies in HIV+ people using longer duration interventions that have high drop-out rates such as exercise (10% drop-out) or yoga (15% drop-out) (32, 93).

The above data have the following implications with respect to statistical power (see Table). The anticipated treatment induced improvement in the glucose disappearance rate of  $30 \pm 23\%$  implies that a sample size of only 16 yields a power of 0.95 (**SA#1**). The expectation that TUDCA will increase D2 expression in muscle by  $2.4 \pm 2.5$  yields a power of 0.85 with 16 subjects per group (**SA#2**). Finally the expected change of  $50 \pm 25\%$  in Grp78 in the TUDCA group implies that only 7 subjects per group are needed to achieve a power of 0.93 (**SA#3**). In summary, our sample size selection implies that the power associated with the glucose disappearance rate (SA#1) and Grp78 (SA#3) will exceed 0.9 while the power associated with D2 expression will be 0.85.

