Study to Understand the Natural History of HIV and AIDS in the Era of Effective Therapy (SUN trial): [name] is Director of the 'SUN' Study. 250 patients are enrolled in this five-year, CDC-funded, longitudinal cohort study to evaluate the metabolic effects of HAART. 53% percent are African American and 26% are women. Enrollment in SUN will facilitate co-enrollment in the current proposal.

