## E 2.C

**Randomization.** Participants will be randomized to TUDCA or placebo. A computer-based randomization scheme will be established, as used in our prior research protocols (90) and *group assignment will be stratified by race and gender. The study statistician, [name], who will be unblinded to group assignment, will provide ongoing oversight to ensure groups are well matched on key characteristics (age, BMI, race, gender).* Capsules containing TUDCA and matching placebo will be made by our research pharmacy, as has been performed in our other placebo-controlled studies (90). The PI, subjects and research technicians will be blinded with respect to group assignment. The coordinator will also be unblinded to group assignment. In the event of an adverse event the coordinator will inform the team and subject of group assignment. [name] RN and [name] RN will be unblinded to ensure that group assignment is known in the case a subject requires urgent medical care.

**Sample Size and statistical power:** All power computations are based on two-sided tests at the 0.05 level of significance for the *primary outcomes* of change of 1) insulin-stimulated glucose disposal (**SA#1**), 2) type 2 deiodinase expression in skeletal muscle (**SA#2**) and 3) Grp78 expression in adipose tissue (**SA#3**) after the intervention.

*Significance of primary outcomes:* Change in insulin-stimulated glucose disappearance is clinically relevant as a predictor of diabetes risk and is highly reproducible in our hands, improving statistical power (91). D2 and Grp78 expression are robust markers of TGR5 activation and ER stress, respectively, and will therefore clarify the mechanisms through which TUDCA may act to improve insulin sensitivity.

*Estimates of change in the primary outcomes:* The estimates for the anticipated changes in the primary endpoints of glucose disposal and D2 expression are based on the prior study conducted in obese, insulin resistant subjects. In this study, glucose rate of disappearance improved by  $30\pm 23\%$  and D2 expression in muscle increased  $2.4\pm 2.5$  fold (Fig 10) after the TUDCA intervention (43). The estimate for the change in Grp78 expression following initiation of TUDCA is based on improvements seen in animal studies with use of TUDCA (52, 53) and in humans after undergoing gastric bypass (92). Based on these findings we estimate a  $50\pm 25\%$  change in Grp78 in the TUDCA group with no change in the placebo group.

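### The primary ANCOVA leaves out race and gender, the randomisation strata, and so gives up some power, mainly for D2, if they predict outcome beyond baseline

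*Combined protocol and SAP*

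**What the plan says.** In E 2.C (Randomization), "group assignment will be stratified by race and gender". The same paragraph asks the statistician to watch balance on age, BMI, race and gender during the trial. The race categories are not defined.

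In G1 (Statistical analysis), the primary model is an ANCOVA of the post-intervention value, in which "the independent variables will be the study group and the baseline value of the outcome". Race and gender appear nowhere else in the analysis, either as primary terms or in a sensitivity analysis, and no reason is given for leaving them out.

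On size and power, E 2.C states that "All power computations are based on two-sided tests at the 0.05 level of significance". G2 adds: "We plan to include 24 subjects in each group and conservatively estimate a 33% drop-out rate". For D2 the assumed effect "yields a power of 0.85 with 16 subjects per group", and for glucose disposal it "implies that a sample size of only 16 yields a power of 0.95".

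**The concern.** Stratified allocation removes chance imbalance in race and gender between the arms, which lowers the true sampling variability of the treatment estimate. A model without the strata leaves their variance in the residual and does not credit that reduction. To the extent that race and gender predict outcome once baseline is in the model, the reported standard error exceeds the true one, confidence intervals are too wide and the test rejects less often than 5% under the null.

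The stake is efficiency and consistency between design and analysis; validity is not in question. The estimate stays unbiased and the error is on the conservative side. D2 is the outcome to watch only because it has the lowest stated power of the three, and so the most room to gain. Nothing in the documents suggests that race or gender matters more for D2 than for the other two.

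**Working it through.** **Inputs from the documents.** Two-sided 5% (E 2.C). 24 per group with 33% drop-out (G2), which gives 24 × 2/3 = 16 per group, or 32 completers. Means and SDs from the G3 table: glucose disposal 0 ± 20 v 30 ± 23; D2 0 ± 1.8 v 2.4 ± 2.5; Grp78 0 ± 0.25 v −0.50 ± 0.25.

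**Reproducing the stated power.** Standardised effect = difference / √((s₁² + s₂²)/2):
- D2: 2.4 / √((1.8² + 2.5²)/2) = 2.4 / 2.178 = 1.10
- Glucose disposal: 30 / √((20² + 23²)/2) = 30 / 21.55 = 1.39
- Grp78: 0.50 / 0.25 = 2.0

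Noncentral t with 16 per group gives 0.854 for D2 (stated 0.85) and 0.968 for glucose disposal (stated 0.95; 0.946 if SD 23 is used in both arms). The D2 figure reproduces, and glucose disposal is within 2 points.

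**Expected gain by formula.** Let R² be the share of post-baseline outcome variance explained by race and gender. Adding them multiplies the residual SD by √(1 − R²). With race at two levels, the error degrees of freedom fall from 29 to 27. The planned standard error is then 1/√(1 − R²) times the adjusted one: 1.05 at R² 0.10, 1.12 at 0.20 and 1.20 at 0.30. D2 power under the adjusted model is 0.852, 0.886, 0.919 and 0.948 at R² 0, 0.10, 0.20 and 0.30, against 0.854 without the strata. This formula ignores imbalance after drop-out, so it somewhat favours adjustment.

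**Simulation, which allows for that imbalance.** 40,000 runs per R²: 48 subjects randomised 1:1 within four race-by-gender strata, then random loss to 32 completers.

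Assumptions not in the documents:
- the R² values, split equally between race and gender
- blocks of 4
- a baseline coefficient of 0.6
- independence of race and gender
- a trial population like the one cohort for which the recruitment section gives a mix: "53% percent are African American and 26% are women"

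The planned model is group + baseline; the adjusted model adds race and gender.

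| R² | Type I error, planned | Reported SE / true SD, planned | D2 power, planned / adjusted | Glucose disposal power, planned / adjusted |
|---|---|---|---|---|
| 0 | 4.8% | 0.99 | 0.838 / 0.826 | 0.961 / 0.955 |
| 0.05 | 4.6% | 1.01 | 0.838 / 0.842 | 0.961 / 0.961 |
| 0.10 | 4.3% | 1.03 | 0.843 / 0.862 | 0.963 / 0.970 |
| 0.20 | 3.8% | 1.06 | 0.851 / 0.898 | 0.968 / 0.983 |
| 0.30 | 3.2% | 1.09 | 0.857 / 0.930 | 0.971 / 0.991 |

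Monte Carlo error is about 0.1 point for type I error and 0.2 point for power. The adjusted model's type I error is 4.9% to 5.0% throughout. Grp78 power is above 0.999 in both models. A second simulation with 8,000 runs per point gave D2 power of 0.844 / 0.862, 0.849 / 0.900 and 0.852 / 0.927 at R² 0.10, 0.20 and 0.30.

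**Break-even.** For D2, adjustment loses 1.2 points at R² = 0 and gains 0.4 point at 0.05. Linear interpolation gives 0.05 × 1.2 / (1.2 + 0.4) ≈ 0.04. Another run put the two models level at about 0.05 (0.834 / 0.833).

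**Cell sizes.** With the cohort's shares, the smallest race-by-gender cell is expected to hold 32 × 0.26 × 0.47 ≈ 4 completers.

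**The case against.** The strongest reply is that the effect rests on an R² the documents do not supply. Each subject's own baseline already absorbs stable differences between subjects, so race and gender must predict the 30-day change to matter. At an R² below about 0.04 to 0.05 the added terms cost power. Nothing in the plan fails: a prespecified two-term ANCOVA with about 32 completers is valid and slightly conservative, and it delivers about the stated power. Glucose disposal, which section D1 treats as the study's primary endpoint, gains less than 1 point at R² 0.10. The simulation uses SDs of change and fold-change as the residual SD of the post value. If the ANCOVA residual is smaller, planned power is higher and the gain smaller. Collapsing race to two levels would also leave part of the stratification out of the model.

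Most of this stands as a limit on size. It does not remove the mismatch: the plan chose race and gender as strata, gives no reason for dropping them from the analysis, and would lose little by keeping them. The downside is about 1 point of D2 power, against about 2 points gained at R² 0.10 and 7 at 0.30. A partly collapsed race term still follows the randomisation more closely than no race term.

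**Conclusion.** The point holds as a conditional efficiency defect. The primary model does not match the stratified randomisation. If race and gender explain residual variance, its test is conservative: type I error is about 4.3% at R² 0.10 and 3.2% at 0.30. The power given up for D2 is about 2 points at R² 0.10, 5 at 0.20 and 7 at 0.30. For glucose disposal it is at most about 2 points, and for Grp78 nil. If the strata explain nothing, adding them costs D2 about 1 point.

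The stated power is not overstated for this reason, and there is no bias or excess false-positive risk. Confidence is medium, because the size depends on an assumed R², block size, baseline coefficient and population mix. The change is worth making before unblinding but is not critical to validity.

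**What to change.** In G1, define the primary ANCOVA for all three primary outcomes as post value = group + baseline value + race + gender. Use main effects only, because the race-by-gender cells are too sparse for an interaction. Keep group + baseline as a sensitivity analysis.

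In E 2.C, state the race levels used for stratification. In G1, carry those levels into the model with a collapsing rule fixed before unblinding, for example the largest category against all others. Fixing it early matters because E 2.C has the statistician unblinded during the trial, so a later choice of covariates would be open to challenge.

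The cost is one sentence in G1 and one definition in E 2.C. With race at two levels, two residual degrees of freedom are spent (29 to 27). No new data are needed, since both factors are already collected for randomisation.

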**G3. Statistical power estimates**

Variable	HIV+ Placebo	HIV+ TUDCA	Power for detecting differences between groups after intervention (30% dropout)
Improvement in insulin-stimulated glucose disposal (%)	0±20	30±23	0.95 (if N=16 per group)
Fold-change in D2 expression after intervention	0±1.8	2.4±2.5	0.85 (if N=16 per group)
Fold-change in Grp 78 expression after intervention	0±0.25	-0.50±0.25	0.97 ( if N=16 per group)

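### The G3 table gives Grp78 a power of 0.97 at 16 per group, but its printed inputs give 0.9998

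*Combined protocol and SAP*

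**What the plan says.** Section E 2.C, under sample size and power, names three primary outcomes, of which Grp78 in adipose tissue is the third. It fixes the test: "All power computations are based on two-sided tests at the 0.05 level of significance". The Grp78 assumption there is a 50±25% "change in Grp78 in the TUDCA group with no change in the placebo group".

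The Grp78 row of the table in G3 carries the same assumption as 0±0.25 for placebo and -0.50±0.25 for TUDCA, and prints a power of "0.97 ( if N=16 per group". The text of G2 uses the same 50±25% and says that "only 7 subjects per group are needed to achieve a power of 0.93". G2 then summarises that power for glucose disposal and Grp78 "will exceed 0.9 while the power associated with D2 expression will be 0.85".

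On attrition, G2 plans 24 per group and says the authors "conservatively estimate a 33% drop-out rate". The header of the power column in G3 reads "Power for detecting differences between groups after intervention (30% dropout".

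**The concern.** G2 and G3 give Grp78 powers of 0.93 at 7 per group and 0.97 at 16 per group from one set of inputs. Power rises with sample size, so the pair looks plausible at first sight. But a trial that already has 0.93 with 7 per group should be very close to 1 with more than twice as many, and a rise of only four points is too small.

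What is at stake is whether the table can be relied on. Grp78 is a declared primary outcome, and G2 sends the reader to the table for the power figures. Someone who checks the cell cannot tell whether the power, the SD, the effect or the sample size is misprinted. If the SD or effect were the wrong entry, the claim for 7 per group would fail too.

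**Working it through.** **Inputs**

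- Two-sided alpha 0.05 (E 2.C).
- Grp78 change: placebo 0, SD 0.25; TUDCA -0.50, SD 0.25 (G3). The TUDCA values agree with the 50±25% in E 2.C and G2.
- 16 per group (G3), and 7 per group for the claim in G2.

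**Method.** Two-sample t-test on the change, equal groups of n:

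- pooled SD = √((s₀² + s₁²)/2)
- standardised difference d = difference / pooled SD
- noncentrality = d × √(n/2), on 2n − 2 degrees of freedom
- power = probability that a noncentral t exceeds the two-sided critical value.

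The planned analysis is ANCOVA on the post-intervention value, but no baseline correlation is given, so a comparison of changes is the calculation that the printed inputs allow.

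**Reproducing the plan's other figures**

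- Grp78 at 7 per group: d = 0.50/0.25 = 2.0; noncentrality 2.0 × √3.5 = 3.742; 12 df; critical value 2.179; power 0.929. Stated 0.93, so it reproduces.
- D2 at 16 per group: pooled SD = √((1.8² + 2.5²)/2) = 2.178; d = 2.4/2.178 = 1.102; noncentrality 1.102 × √8 = 3.116; power 0.854. Stated 0.85, so it reproduces.
- Glucose disposal at 16 per group, printed as "0.95 (if N=16 per group": the printed SDs of 20 and 23 give 0.968, and SD 23 in both arms gives 0.946. The stated figure lies between the two.

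**The Grp78 cell.** At 16 per group, d = 2.0; noncentrality 2.0 × √8 = 5.657; 30 df; critical value 2.042; power **0.9998**. Stated 0.97.

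| n per group | Grp78 power (d = 2.0) |
|---|---|
| 7 | 0.929 |
| 8 | 0.960 |
| 9 | 0.978 |
| 16 | 0.9998 |

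With these inputs power passes 0.97 between 8 and 9 per group.

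**Could another convention give 0.97 at 16 per group?**

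| Variant | Power |
|---|---|
| Normal approximation | 0.9999 |
| One-sided 0.05 | 0.99995 |
| Two-sided 0.05/3 (three primary outcomes) | 0.9986 |
| Two-sided 0.01 | 0.9971 |
| 17 per group (16.8 completers at 30% dropout, rounded up) | 0.9999 |
| Rank test, 10,000 simulated trials | 0.9995 |

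None comes near. A power of 0.97 at 16 per group needs d = 1.404, which means an SD of 0.356 in both arms with a change of 0.50, or a change of 0.351 with SD 0.25. Neither is stated. At d = 1.404, moreover, 7 per group would have power of only 0.67, so the 0.93 in G2 would be lost.

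**Dropout.** 24 × (1 − 0.33) = 16.1 and 24 × (1 − 0.30) = 16.8. The difference does not explain the 0.97.

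**The case against.** The strongest reply is that nothing turns on this. The error is conservative. The only statement in the text about Grp78 at the chosen sample size, that power exceeds 0.9, is true at 0.97 and at 0.9998. D2, at 0.85, has the lowest power of the three outcomes, so Grp78 does not drive the choice of 24 per group. All of that stands, and it sets the weight of the point.

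It can also be said that 0.93 at 7 and 0.97 at 16 do not contradict each other on their face, because the sample sizes differ. That is fair: the conflict appears only on recomputation. It is still a conflict, since no single value of d gives both figures.

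A third argument is that the wrong entry might be an input and not the power. A placebo SD of about 0.44 with a TUDCA SD of 0.25 would also give 0.97 at 16 per group, and the placebo SD is printed only in G3. But that reading contradicts the printed 0.25 and breaks the 0.93 at 7 per group, which the printed inputs reproduce. The printed inputs are the likelier reading. What survives is that the documents do not show where 0.97 came from, so the authors should confirm the inputs when they correct the cell.

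On dropout, 16.8 completers rounded down is also 16, so N=16 does not prove that the header's 30% is the wrong figure. The two percentages still differ and should be made to agree.

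**Conclusion.** The point holds. From the row's own inputs, Grp78 power at 16 per group is 0.9998 and not 0.97, an understatement of about 3 percentage points. In terms of missing the assumed effect, the table implies a 3% chance and the inputs imply about 0.02%. The 0.93 at 7 per group in G2 is correct.

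This rests on a two-sided two-sample t-test of the change at 0.05 with the printed means and SDs. That method reproduces the Grp78 figure in the text and the D2 figure. It does not depend on whether the assumed 50±25% is realistic.

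The sample size, the planned analysis and the conclusion that Grp78 power exceeds 0.9 are unaffected. The 30% against 33% dropout is a separate, minor inconsistency in the same table.

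**What to change.** In G3, change the Grp78 power at 16 per group to >0.99, and keep 0.93 at 7 per group in G2. If a different SD or effect was intended, state it and recompute both figures. Make the dropout figure in the G3 column header agree with G2; 33% gives 16.1 completers and fits N=16 directly.

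Optionally, for glucose disposal, either print 0.97, which follows from the SDs of 20 and 23 in the row, or note that 0.95 corresponds to SD 23 in both arms. The D2 entry needs no correction.

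The cost is one table cell and one figure in a column header, with no new data, no more participants and no change to the analysis.

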**Study Timetable:**

	Subjects
Year 1	8
Year 2	12
Year 3	12
Year 4	12
Year 5	4
Total studies	48

## **H. Protection of human subjects.**

**H1. Risk to subjects.** Blood and tissue samples will be collected from all subjects. The specimens will be obtained solely for research purposes. Study samples and data sheets will be coded with an identification number for each subject. All of the data from individual subjects will be maintained confidentially and their names and identities will not be disclosed in any published document. The PI, coordinator and [name] are covered by a certificate of confidentiality carried by the ACTU.

Potential risks of the study include: 1) the risks of catheter insertion and blood drawing include discomfort, bleeding or infection at the site of insertion; 2) the infusion of hormones may cause changes in blood glucose and may cause nausea, however, blood glucose is monitored throughout the study; 3) biopsies of muscle and adipose tissue can cause pain, bleeding, and infection; 4) magnetic resonance spectroscopy and MRI can be harmful for people with metal implants in their bodies, and may cause discomfort in people with claustrophobia; (those with implants or history of claustrophobia will be excluded); 5) if an arterial line is placed, a blood clot can occur at the site of the catheter insertion and could decrease blood flow to the hand causing tissue damage (however, the risk of this is extremely small because only a small size catheter is used and it is kept in for a short period of time; furthermore, before catheter placement, the hand is examined to ensure adequate blood flow); 6) the risks of infusing stable isotope tracers include the possibility of pyrogen response or infection; however, all solutions will be tested for pyrogens and sterility before infusion and will be administered under strict aseptic conditions; there are no known short- or long-term risks associated with the infusion of the isotopes themselves; 7) the effect of TUDCA on ART absorption and handling is not known therefore we will enrol only subjects with controlled HIV and will monitor CD4 counts and viral load upon completion of this brief study. These results will be reviewed by the DSMB to ensure patient safety.

**Adequacy of protection against risks.** All experimental procedures will be explained in writing and orally to the subject by the principal investigator, co-investigator, or the research coordinator. Written informed consent will be obtained after all questions have been answered and the risks and benefits of participation in the study have been described. The objectives of the project, all of the requirements for participation, and any possible discomforts and risks will be clearly explained to each subject orally and in writing in lay terms that he/she is able to comprehend. The subject must sign a consent form, approved by the Washington University School of Medicine Institutional Review Board, before participating in any aspect

of the study. To secure data transfer between WUMS and VUMS, a Secure File Transfer system will be used to transmit any PHI or study-related data. An original copy of each consent will be kept on file at the primary site with an additional signed consent at VUMS. At each site all data will be kept within a secure server and will be deidentified at the closure of the study.

**H2 Compliance Program:** During the intervention, subjects will be seen weekly by a member of the research team who will take weight, measure blood pressure and pulse, review any problems and verify compliance by using a pill count. Should the need for medical evaluation arise, they will be seen by the PI, [name], [name], [name] all of whom are certified in Internal Medicine.

Should the need for medical attention arise all the resources of a large teaching hospital at each site are available for subject evaluation and treatment. Complete physical examinations will be performed to screen out subjects who may be at potential risk. Subjects will be carefully monitored by the medical staff associated with the study for the duration of the study.

Potential benefits of the proposed research to the subjects and others. Potential benefits to the subjects participating in the study include information regarding their medical health, and screening for diabetes. Benefits to society include a better understanding of the factors responsible for insulin resistance in HIV and the mechanisms through which bile acids may improve these outcomes.

Importance of the knowledge to be gained. This study will provide important information regarding the causes of insulin resistance in HIV and will test the efficacy of a new modality. The risks associated with this research are minimal relative to the clinical implications of this study, which could lead to better therapies for preventing and treating the metabolic complications of PI-ART.

**H3 Data and safety monitoring.** Data from the study will be monitored on a continuous basis by the PI, co-investigators, study research nurse, and research coordinator. The PI, study research nurse, research coordinator, and postdoctoral research fellow will meet weekly to review any study issues. The PI, study research nurse, and research coordinator will review all serious adverse events (SAEs), adverse events (AEs), and laboratory values. [name], the study research nurse and coordinator at VUMS will also discuss weekly eligible or enrolled subjects. In the event of an SAE or reportable event, [name] or [name] will contact [name] within 24 hours. The Washington University Human Research Protection Office (HRPO) will be notified as a reportable event within 10 days of knowledge of the event. Follow-up will be performed as additional information becomes available. In addition, all laboratory values outside of normal range which place the participant at risk are discussed with the study participant and appropriate arrangements will be made for treatment, if necessary. Data from the study will be monitored on a continuous basis by the PI, co-investigators, research coordinator, and research study nurse.

A Data and Safety Monitoring Board, consisting of [name]. (Gastroenterologist), [name]. (Gastroenterologist), and [name]. (Infectious Diseases), will be available for discussion at any time with the PI to review any safety issues. All data will be treated confidentially and the subjects' names and identities will not be disclosed in any published reports. The subjects will be informed orally and in writing that they are free to withdraw from the study at any time with no bias or prejudice. The data obtained from this study will be kept confidential and no subjects will be identified in any written publications. Patients are assigned a study specific identifying number upon entry to the study, after which all medical information is referenced by this number. Clinic records are maintained in locked file cabinets within a locked room.

Tauroursodeoxycholic acid for protease-inhibitor associated insulin resistance  
PI: [name]

